13.3 Deaths

All reported deaths will be summarized by cohort and cause of death. A by-subject listing that includes date of death and cause of death will be provided.

13.4 Laboratory Assessments

13.4.1 Data Summary Methods

All laboratory values will be converted to and reported as SI units and classified as normal, low, or high based on the normal ranges provided by the local laboratory.

Hematologic parameters, including platelet counts, hemoglobin, and neutrophils, will be summarized by IWCLL 2008 ([Appendix C](#)) and NCI CTCAE v4.03 respectively. All other gradable laboratory parameters will be graded using the NCI CTCAE v4.03.

Per the grading scale in the IWCLL guidelines, ANC: Both baseline grade and post-baseline grade are defined based on absolute values and 2) Hemoglobin and platelet: baseline grade is not applicable (no criterion is provided to define baseline grade) and post-baseline grade is based on percentage decrease from baseline value.

Gradable parameters that have criteria available for both low and high values (e.g., hypercalcaemia for a high value of calcium and hypocalcaemia for a low value of calcium) based on the NCI CTCAE v4.03 will be summarized for both criteria (low and high).

Subjects will be counted only once for each criterion/direction. The same subject can be counted for both criteria if the subject has laboratory values meeting each criterion. Subjects meeting the criteria for Grade 1 or higher for the high direction will be summarized under Grade 0 when summarizing the low direction and vice versa.

For each laboratory parameter, the baseline laboratory value/grade is defined as the last laboratory value/grade collected on or prior to the date of the first dose of study drug. The change from baseline to post-baseline value will be calculated for each parameter.

13.4.2 T/B/NK Cell Counts

Descriptive statistics will be presented at baseline, last post-baseline, minimum post-baseline, and maximum post-baseline for the flow cytometry testing parameters (CD3⁺, CD4⁺, CD8⁺, , CD19⁺, and NK cells).

Changes from baseline at each of the last, minimum, and maximum post-baseline time points will be summarized. Figures will be presented for the mean of selected parameters over time as appropriate.

13.4.3 Serum Immunoglobulin

For IgG, IgM, and IgA levels, descriptive statistics will be presented at baseline, last post-baseline, minimum post-baseline, and maximum post-baseline. Changes from baseline at each of the last, minimum, and maximum post-baseline time points will be summarized. Figures will be presented for the mean of selected parameters over time as appropriate.

13.4.4 Analysis of Lymphocytosis

Lymphocytosis is defined as an elevation in ALC of $\geq 50\%$ compared with baseline and a post-baseline assessment $> 5,000/\mu\text{L}$.

The number, percentage (and 95% exact binomial CI) of subjects with at least once occurrence of lymphocytosis will be summarized.

Time to Lymphocytosis will be calculated from the date of the first dose of study drug to the first post-baseline ALC which met the lymphocytosis criteria and summarized using descriptive statistics.

Duration of lymphocytosis (DOL) is defined as the duration of time from the earliest date on which the ALC value met the lymphocytosis criteria at a post-baseline assessment to the earliest date on which a subsequent ALC value met the resolution criteria. Resolution of lymphocytosis is defined as 1) a decrease of ALC value to the baseline level or lower or 2) an achievement of ALC value that is below 5,000/ μ L, whichever occurs first.

DOL = Earliest date of meeting resolution criteria - Earliest date of meeting lymphocytosis criteria + 1.

Confirmation is not required for resolution of lymphocytosis. Subjects who developed lymphocytosis but whose lymphocytosis was not resolved prior to the analysis cutoff date will be censored at the last sample date with non-missing ALC value at or prior to the analysis cutoff date. KM curves will be used to estimate the distribution of DOL. The 50th percentile of KM estimates along with its two-sided 95% CI will be used to estimate the median DOL.

13.5 Vital Signs and Physical Examinations

For each vital sign measurement, descriptive statistics will be presented at baseline, last post-baseline, minimum post-baseline, and maximum post-baseline. Change from baseline at each of the last, minimum, and maximum post-baseline time points will be summarized.

Findings of abnormal physical examinations at baseline and post-baseline will be tabulated by body system at each visit.

Shift of blood pressure from baseline to the worst score during the treatment will be provided as shift tables.

13.6 ECOG Performance Status

Shift of ECOG from baseline to the worst score during the treatment will be summarized in a shift table.

15.0 APPENDICES

Appendix A: Analysis Windows

Tumor assessment/CT/SPD For Cohort 1 and 2				
			Analysis Window (Study Day)	
Nominal Visit	Study Day	Nominal Month	Lower (inclusive)	Upper (inclusive)
C4D1	85	0		127
C7D1	169	1	128	211
C10D1	253	1	212	281
C12D1	309	1	282	351
C15D1	393	13	352	435
C18D1	477	15	436	519
C21D1	561	18	520	603
C24D1	645	21	604	687
C30D1	813	27	688	855
C36D1	981	32	856	

Tumor assessment/CT/SPD For Cohort 3 and 4				
			Analysis Window (Study Day)	
Nominal Visit	Study Day	Nominal Month	Lower (inclusive)	Upper (inclusive)
C4D1	85	0		127
C7D1	169	1	128	211
C10D1	253	1	212	295
C13D1	337	1	296	379
C16D1	421	13	380	463
C19D1	505	15	464	547
C22D1	589	18	548	617
C24D1	645	21	618	687
C30D1	813	27	688	855
C36D1	981	32	856	

Hematology / Chemistry				
			Analysis Window (Study Day)	
Nominal Visit	Study Day	Nominal Month	Lower (inclusive)	Upper (inclusive)
C1D1	1	0		1
C1D8	8	1	2	12
C1D15	15	1	13	21
C2D1	29	1	22	43
C3D1	57	2	44	71
C4D1	85	2	72	99
C5D1	113	3	100	127
C6D1	141	4	128	155
C7D1	169	5	156	183
C8D1	197	6	184	211
C9D1	225	7	212	239
C10D1	253	8	240	267
C11D1	281	9	268	295
C12D1	309	10	296	351
C15D1	393	13	352	435

C18D1	477	15	436	519
C21D1	561	18	520	603
C24D1	645	21	604	687
C30D1	813	27	688	855
C36D1	981	32	856	

Physical Examination/ECOG				
			Analysis Window (Study Day)	
Nominal Visit	Study Day	Nominal Month	Lower (inclusive)	Upper (inclusive)
C1D1	1	0		1
C1D8	8	1	2	12
C1D15	15	1	13	21
C2D1	29	1	22	43
C3D1	57	2	44	71
C4D1	85	2	72	99
C5D1	113	3	100	127
C6D1	141	4	128	155
C7D1	169	5	156	183
C8D1	197	6	184	211
C9D1	225	7	212	239
C10D1	253	8	240	267
C11D1	281	9	268	295
C12D1	309	10	296	351
C15D1	393	13	352	435
C18D1	477	15	436	519
C21D1	561	18	520	603
C24D1	645	21	604	687
C30D1	813	27	688	855
C36D1	981	32	856	

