the reduction guidelines in [Table 9](#). Missed doses should not be made up. Subjects who are stable at a lower dose for [CCI](#) may be dose-escalated by 1 dose level.

For Grade ≥ 3 nonhematologic toxicity in Cycles 1 and 2 or despite following recommendations for venetoclax, please follow the guidelines noted in [Section 7.2.2](#) for acalabrutinib and/or obinutuzumab.

For \geq Grade 3 nonhematologic toxicity for which individual study drug attribution is not possible, subjects should have all drugs held until toxicity resolves to \leq Grade 1, and then subjects should be restarted at 1 dose level lower again using [Table 10](#). Subjects who are stable at a lower dose level for [CCI](#) may be dose-escalated by 1 dose level.

Table 9: Dose Modification for Toxicity During Venetoclax Treatment (Cohorts 3 and 4)

Dose at Interruption, mg	Restart Dose, mg ^a
CCI	

^a During the [CCI](#) continue the reduced dose for [CCI](#) before increasing the dose.

Table 10: Dose Adjustments for All Other Nonhematologic Toxicities for Which Individual Study Drug Attribution is Not Possible (All Cohorts)

Dose Level	Acalabrutinib Dose	Rituximab Dose	Obinutuzumab Dose	Venetoclax ^a
CCI				

^a During the [CCI](#) continue the reduced dose for [CCI](#) before increasing the dose.

8 Schedule of Activities

Table 11. Schedule of Activities: Cohorts 1 and 2

Tests & Observations (all labs listed here are standard of care except those labeled correlative studies and PK)	Screening	Day 1, 8, 15 of Cycle 1	Day 2 of Cycle 1	Day 1 of Cycles 2-12	Day 1 of Cycles 15, 18, 21, 24 ^H	Relapse/ Disease progression	Safety Follow-up ^I	Discontinua- tion Follow-up ^J	Long-term Follow-up ^K
ACP-196 CCI ¹ PO administration		CCI							
Obinutuzumab administration									
History & physical examination with tumor measurements ¹	X	X		X	X	X	X		
Height	X								
Weight	X	X		X	X	X	X		
ECOG PS	X	X		X	X	X	X		
2 buccal swabs	X								
ECG ²	X								
Concomitant medications	X	X	X	X	X	X	X	X	
Adverse events	X	X	X	X	X	X	X	X	
FISH/stimulated karyotype ³	X					X			
Zap-70 methylation ⁴	X								
IGHV mutational status ⁴	X								
Complete blood count (CBC)	X	X		X	X	X	X		
Chem 10	X	X		X	X		X		
Liver function panel	X	X		X	X		X		
LDH, uric acid	X	X		X	X		X		
Beta-2-microglobulin	X								
Direct antiglobulin test (Coomb's test)	X								

Table 11. Schedule of Activities: Cohorts 1 and 2

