 - B. Response evaluations will be done every 12 weeks from randomization for the first 24 months (with the 4th evaluation shifted to Cycle 12 Day 1 rather than Cycle 13 Day 1, to align with study visits), and then every 24 weeks thereafter. Hematology results must be done within 7 days of CT scans. Bone marrow biopsies/aspirates to confirm a CR must be done within 4 weeks of the CT scan, which showed CR.
 - C. PB samples will be used to evaluate for MRD every 3 cycles (at the discretion of the investigator, in line with scheduled response assessments, per protocol).
 - D. Specific times and tube types for correlative samples are outlined in [Section 13.2](#).
 - E. PK analysis will be performed on the first 8 expansion group patients of Cohort 1. Schedule can be found in [Section 13.3](#).
 - F. If performed as part of relapse analysis
 - G. As outlined in [Section 13.4](#)
 - H. Visits to continue every 6 cycles thereafter (\pm 7 days).
 - I. A safety follow-up (SFU) visit is required for all subjects 30 days (+7) from the last dose of study drug.
 - J. After discontinuation of study treatment for any reason, each subject should be followed until disease progression or the start of alternative anticancer therapy. If disease progression has not occurred at the time of the 30-day SFU visit, discontinuation follow-up (DFU) visits should occur approximately every 12 weeks until disease progression. During this period, subjects will be followed via CT scans every 24 weeks; after 2 years in DFU, CT scans will be yearly. AE and concomitant medication reporting, irrespective of seriousness, ends 30 days after the last dose of study drug(s).
 - K. After disease progression or the start of alternative anticancer therapy, all subjects (unless they have withdrawn consent) will be contacted approximately every 12 weeks by telephone, to assess survival until death or lost to follow up.

Table 12: Schedule of Assessments – Cohort 3

Day	Screening	Treatment Phase & Response Evaluation												SFU	Discontinuation follow-up ¹	Relapse/ Disease Progression	Long-term follow-up	
		Cycle 1		Cycle 2			Cycle 3			Cycles 4 -7	Cycles 10, 13, 16, 19, 22	Cycle 24	Cycle 24 q6 cycles					
		1	15	1	8	15	22	1	8	15	22	1	1	1	1			
Study Windows (days)	-28	±3		±3				±3				±3	±3	±3	±7	+7	±7	±7
Study Drug Administration ¹		CCI																
Acalabrutinib																		
Rituximab																		
Venetoclax																		
Procedures																		

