- 10 mL bone marrow in a heparin tube, which will be processed by Ficoll density gradient centrifugation and viably frozen
- Peripheral blood 4 x 8.5 mL ACD tubes, which will be processed by Ficoll density gradient centrifugation and viably frozen
- Peripheral blood 2 x 6 mL EDTA tubes that will be centrifuged to obtain plasma
- If applicable, sample of lymph node biopsy to confirm transformation or relapse, which will be processed to a mononuclear cell suspension using manual disassociation and Ficoll density gradient centrifugation or red cell lysis.

13.2.2 Cohorts 3 and 4

Refer to the Schedules of Assessments ([Table 12](#) and [Table 13](#)).

CCI

CCI

Cell Death Protein Ratio Flow

Blood samples will be collected and analyzed within 48 hours of collection using flow cytometry for cell death proteins and pathway and/or disease-related proteins. Samples should consist of a 10-mL blood draw to be obtained at the following time points:

[figure not shown]
- Screening
- Cycle 1 Day 1, before acalabrutinib dose
- Cycle 2 Day 1, before anti-CD20 antibody
- Cycle 3 Day 1, before venetoclax
- Relapse/PD
- Safety Follow-up Visit

Immunophenotyping

Blood samples will be collected to evaluate tumor and immune microenvironment by flow cytometry. Samples should consist of a 10-mL blood draw to be obtained at the following time points:

- Screening
- Cycle 1 Day 1, before acalabrutinib dose
- Cycle 2 Day 1, before anti-CD20 antibody
- Cycle 3 Day 1, before venetoclax
- Relapse/PD
- Safety Follow-up Visit

CCI

On-treatment Bone Marrow

Remaining bone marrow will be analyzed to confirm findings from correlative analysis from peripheral blood samples. If bone marrow is being collected, surplus could be submitted for correlative analysis.

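### The laboratory and physical-examination windows in SAP Appendix A follow the Cohort 1/2 calendar, so by-visit output for Cohorts 3/4 is mislabelled

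*SAP*

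**What the plan says.** SAP 7.3 assigns each assessment to an analysis visit by the window its date falls in. It sets no cohort condition and does not say what to do when several records fall in one window. SAP 7.1 presents tables by cohort.

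Appendix A then gives four window tables. Two are for tumor assessments, one of them headed "Tumor assessment/CT/SPD For Cohort 3 and 4", with rows such as "C13D1 337 1 296 379". The other two, Hematology/Chemistry and Physical Examination/ECOG, carry no cohort label. Both contain "C12D1 309 10 296 351" followed by "C15D1 393 13 352 435".

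Protocol Table 11 (Cohorts 1 and 2) schedules "Day 1, 8, 15 of Cycle 1", then "Day 1 of Cycles 2-12", then Cycles 15, 18, 21 and 24 and every 6 cycles after that. Tables 12 and 13 (Cohorts 3 and 4) schedule Cycle 1 Days 1 and 15, four visits in each of Cycles 2 and 3, Cycles 4 to 7, "Cycles 10, 13, 16, 19, 22", Cycle 24, and then every 6 cycles. The venetoclax start is redacted in the treatment sections, but protocol 13.2.2 lists a sample at "Cycle 3 Day 1, before venetoclax".

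**The concern.** The unlabelled tables match the Table 11 calendar visit for visit, yet SAP 7.3 applies them to everyone. A Cohort 3/4 by-visit table would show visits that those cohorts never have, and would omit visits that they do have. On one and the same day, the CT and the physical examination would carry different visit names.

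The second issue is in the laboratory data around the start of venetoclax. Tables 12 and 13 add draws in Cycles 2 and 3, and the single table has no rows for them, so they fall into neighbouring Day 1 windows. Safety is the primary objective in Cohorts 3 and 4, with 12 subjects in each. A by-visit display whose C3D1 row could hold values from before and after the first venetoclax dose would be hard to interpret.

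**Working it through.** **Inputs.** Windows: SAP Appendix A. Visit days: protocol Tables 11, 12 and 13. Cycle length: 28 days, from protocol 6.5 (8 weeks equals 2 cycles) and from Appendix A itself (C2D1 is Day 29). Laboratory tolerance: ±3 days, Tables 12 and 13, footnote 7. Venetoclax start: Cycle 3 Day 1, inferred from protocol 13.2.2 and consistent with protocol 7.2.1.2, which handles Cycles 1 and 2 separately from the period after venetoclax starts.

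**Formula.** Study day = 28 × (cycle − 1) + day of cycle. A window edge is the midpoint between adjacent visits.

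**Reproducing the plan's row.** C12D1 = 28 × 11 + 1 = 309. Lower edge: (281 + 309)/2 = 295, so the window opens on Day 296. Upper edge: (309 + 393)/2 = 351. This matches 296-351. Day 393 is C15D1, so the row assumes the Cohort 1/2 calendar.

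**Late Cohort 3/4 visits under the stated windows.**

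| Visit | Study day | Lab and exam label (window) | Tumor label, Cohorts 3/4 (window) |
|---|---|---|---|
| C13D1 | 28 × 12 + 1 = 337 | C12D1 (296-351) | C13D1 (296-379) |
| C16D1 | 28 × 15 + 1 = 421 | C15D1 (352-435) | C16D1 (380-463) |
| C19D1 | 28 × 18 + 1 = 505 | C18D1 (436-519) | C19D1 (464-547) |
| C22D1 | 28 × 21 + 1 = 589 | C21D1 (520-603) | C22D1 (548-617) |

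Each label is one cycle early (337 − 309 = 28, and likewise for the other three). Moving a visit by ±3 days changes none of the four.

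**Cycle 2-3 laboratory draws.**

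| Window | Cohort 3 draws (day) | Cohort 4 draws (day) |
|---|---|---|
| C2D1 (22-43) | C2D1 (29), C2D8 (36), C2D15 (43) | C2D1 (29), C2D2 (30), C2D8 (36), C2D15 (43) |
| C3D1 (44-71) | C2D22 (50), C3D1 (57), C3D8 (64), C3D15 (71) | C3D1 (57), C3D8 (64), C3D15 (71) |
| C4D1 (72-99) | C3D22 (78), C4D1 (85) | C3D22 (78), C4D1 (85) |

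With venetoclax starting on Day 57, the C3D1 window holds two pre-venetoclax draws in Cohort 3 (Day 50 and the pre-dose draw on Day 57) and one in Cohort 4 (Day 57). Two on-venetoclax draws (Days 64 and 71) join them in each cohort. Days 43 and 71 are upper edges: a draw one day late, within tolerance, moves C2D15 into C3D1 or C3D15 into C4D1.

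**Count.** Through Cycle 36 each cohort has 10 laboratory days in Cycles 1-3 and 12 later, 22 in all. Ten fall in another visit's window (6 in Cycles 2-3 and 4 late). For physical examinations, 4 of 15 scheduled visits are mislabelled. Cycle 2 and 3 examinations fall on Day 1, so the venetoclax mix does not arise there. The C1D8, C8D1, C9D1 and C11D1 windows match no visit in Tables 12 or 13.

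**The case against.** The strongest reply is that little planned output depends on these windows. SAP 13.4.1 specifies normal-range classification, toxicity grades and change from baseline, and names no by-visit hematology or chemistry table. Vital signs use last, minimum and maximum values, ECOG uses a worst-score shift, and lymphocytosis uses actual dates. The only named by-visit output affected is the physical-examination table in SAP 13.5. This stands. A by-visit laboratory summary is only implied, because SAP 7.3 reserves windows for parameters summarized by visit.

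A reader might also infer that pre- and on-venetoclax values will be averaged together. The documents do not say so. A closest-to-target rule would select Day 57 whenever that draw exists and remove most of the mix. But no such rule is stated. If the Day 57 draw were missing in Cohort 3, Days 50 and 64 would tie at 7 days each, one before and one after venetoclax. Nor would the rule correct the late labels.

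The late-visit error is a uniform one-cycle offset. Each of the four visits sits alone in its window, no scheduled value is lost, and cohorts are tabulated separately, so labels do not blend cohorts.

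**Conclusion.** Wrong as written; low impact. The stated rule gives wrong labels for four late visits in both cohorts, and it contradicts the Cohort 3/4 tumor windows in the same appendix. It also places six Cycle 2-3 laboratory draws per cohort in another visit's window. The pre/on-venetoclax overlap concerns laboratory values only and is clearest in Cohort 3.

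A reader might infer that the primary safety results of Cohorts 3/4 are compromised. They are not: treatment-emergent events, worst grades, deaths, shift tables and last/minimum/maximum summaries do not use these windows. Nor is a comparison of laboratory values before and after venetoclax a stated objective.

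The mapping assumes nominal 28-day cycles and a venetoclax start on Cycle 3 Day 1. Protocol 6.1.2.1 and 6.1.2.2 allow cycle starts to shift, so actual days may drift. One further inconsistency bears on the empty C1D8 window: protocol 7.2.1.2 describes weekly Cycle 1 laboratory monitoring for Cohorts 3/4, whereas Tables 12 and 13 list Days 1 and 15 only.

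**What to change.** 1. Add Cohort 3/4 tables for Hematology/Chemistry and for Physical Examination/ECOG, keyed to protocol Tables 12 and 13. Midpoint windows are C10 212-295, C13 296-379, C16 380-463, C19 464-547 and C22 548-617, identical to the existing Cohort 3/4 tumor windows. C7 then runs 156-211.
2. For laboratory data, add the Cycle 2-3 days by cohort. Cohort 3: C2D22 47-53 and C3D1 54-60. Cohort 4: C2D15 40-50 and C3D1 51-60. Both: C3D8 61-67, C3D15 68-74, C3D22 75-81 and C4D1 82-99.
3. Classify laboratory values as pre- or on-venetoclax by each subject's actual first venetoclax dose, counting the C3D1 pre-dose draw as pre-venetoclax. Fixed study-day windows cannot guarantee this split when cycles shift.
4. In the Physical Examination/ECOG table, list only days on which those assessments are scheduled.
5. State in SAP 7.3 how one record is chosen when several fall in a window, for example the closest to the target day, with a tie-break.
6. Reconcile the Cycle 1 laboratory frequency in protocol 7.2.1.2 with Tables 12 and 13 before deciding whether to keep a C1D8 laboratory window.

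The cost is the added window tables, a sentence or two in SAP 7.3, and reprogramming of the visit map. No new data are needed.

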Appendix B: Rai Stage Derivation Criteria

Stage	Lymphocytosis	Lymphadenopathy	Hepatomegaly or splenomegaly	Anemia	Thrombocytopenia
0	1	0	0	0	0
I	1	1	0	0	0
II	1	any	1	0	0
III	1	any	any	1	0
IV	1	any	any	any	1

1 = yes, 0 = no, any = yes or no

[figure not shown]
Appendix C: Grading Scale for Hematologic Toxicity in CLL (Hallek 2008)

Grade ¹	Decrease in platelets ² or Hb ³ (nadir) from pretreatment value	Absolute neutrophil count/ μ L ⁴ (nadir)
0	No change to 10%	≥ 2000
1	11%-24%	≥ 1500 and < 2000
2	25%-49%	≥ 1000 and < 1500
3	50%-74%	≥ 500 and < 1000
4	$\geq 75\%$	< 500

1. Grades: 1, mild; 2, moderate; 3, severe; 4, life-threatening; 5, fatal. Death occurring as a result of toxicity at any level of decrease from pretreatment will be reported as Grade 5.
2. Platelet counts must be below normal levels for Grades 1 to 4. If, at any level of decrease, the platelet count is $< 20 \times 10^9/L$ (20,000/ μ L), this will be considered Grade 4 toxicity, unless a severe or life-threatening decrease in the initial platelet count (e.g., $< 20 \times 10^9/L$ [20,000/ μ L]) was present pretreatment, in which case the patient is not evaluable for toxicity referable to platelet counts.
3. Hemoglobin (Hb) levels must be below normal levels for Grades 1 to 4. Baseline and subsequent Hb determinations must be performed before any given transfusions. The use of erythropoietin is irrelevant for the grading of toxicity but should be documented.
4. If the ANC reaches $< 1 \times 10^9/L$ (1000/ μ L), it should be judged to be Grade 3 toxicity. Other decreases in the white blood cell count or in circulating neutrophils are not to be considered because a decrease in the white blood cell count is a desired therapeutic endpoint. A gradual decrease in granulocytes is not a reliable index in CLL for stepwise grading of toxicity. If the ANC was $< 1 \times 10^9/L$ (1000/ μ L) before therapy, the patient is not evaluable for toxicity referable to the ANC. The use of growth factors such as granulocyte colony-stimulating factor (G-CSF) is not relevant to the grading of toxicity but should be documented.

Appendix D: Defining Prior and Concomitant Medication Flags

The figure below depicts various scenarios of prior and concomitant medications. The prior and concomitant medication flags are specified respectively for each scenario.

Appendix E: Patient Reported Outcomes (PRO)

1. EORTC QLQ-C30

The United States English version is provided as an example only.

EORTC QLQ-C30 (version 3)

We are interested in some things about you and your health. Please answer all of the questions yourself by circling the number that best applies to you. There are no "right" or "wrong" answers. The information that you provide will remain strictly confidential.

Please fill in your initials:

Your birthdate (Day, Month, Year):
Today's date (Day, Month, Year):

31

	Not at All	A Little	Quite a Bit	Very Much
1. Do you have any trouble doing strenuous activities, like carrying a heavy shopping bag or a suitcase?	1	2	3	4
2. Do you have any trouble taking a long walk?	1	2	3	4
3. Do you have any trouble taking a short walk outside of the house?	1	2	3	4
4. Do you need to stay in bed or a chair during the day?	1	2	3	4
5. Do you need help with eating, dressing, washing yourself or using the toilet?	1	2	3	4

During the past week:

	Not at All	A Little	Quite a Bit	Very Much
6. Were you limited in doing either your work or other daily activities?	1	2	3	4
7. Were you limited in pursuing your hobbies or other leisure time activities?	1	2	3	4
8. Were you short of breath?	1	2	3	4
9. Have you had pain?	1	2	3	4
10. Did you need to rest?	1	2	3	4
11. Have you had trouble sleeping?	1	2	3	4
12. Have you felt weak?	1	2	3	4
13. Have you lacked appetite?	1	2	3	4
14. Have you felt nauseated?	1	2	3	4
15. Have you vomited?	1	2	3	4

Please go on to the next page

During the past week:	Not at All	A Little	Quite a Bit	Very Much
16. Have you been constipated?	1	2	3	4
17. Have you had diarrhea?	1	2	3	4
18. Were you tired?	1	2	3	4
19. Did pain interfere with your daily activities?	1	2	3	4
20. Have you had difficulty in concentrating on things, like reading a newspaper or watching television?	1	2	3	4
21. Did you feel tense?	1	2	3	4
22. Did you worry?	1	2	3	4
23. Did you feel irritable?	1	2	3	4
24. Did you feel depressed?	1	2	3	4
25. Have you had difficulty remembering things?	1	2	3	4
26. Has your physical condition or medical treatment interfered with your family life?	1	2	3	4
27. Has your physical condition or medical treatment interfered with your social activities?	1	2	3	4
28. Has your physical condition or medical treatment caused you financial difficulties?	1	2	3	4

For the following questions please circle the number between 1 and 7 that best applies to you

29. How would you rate your overall health during the past week?

1 2 3 4 5 6 7

30. How would you rate your overall quality of life during the past week?

1 2 3 4 5 6 7

Table 1 EORTC QLQ-C30 Scoring Guide

	Scale	Number of items	Item range*	Version 3.0 Item numbers	Function scales
Global health status / QoL					
Global health status/QoL (revised)†	QL2	2	6	29, 30	
Functional scales					
Physical functioning (revised)†	PF2	5	3	1 to 5	F
Role functioning (revised)†	RF2	2	3	6, 7	F
Emotional functioning	EF	4	3	21 to 24	F
Cognitive functioning	CF	2	3	20, 25	F
Social functioning	SF	2	3	26, 27	F
Symptom scales / items					
Fatigue	FA	3	3	10, 12, 18	
Nausea and vomiting	NV	2	3	14, 15	
Pain	PA	2	3	9, 19	
Dyspnoea	DY	1	3	8	
Insomnia	SL	1	3	11	
Appetite loss	AP	1	3	13	
Constipation	CO	1	3	16	
Diarrhoea	DI	1	3	17	
Financial difficulties	FI	1	3	28	

* *Item range* is the difference between the possible maximum and the minimum response to individual items; most items take values from 1 to 4, giving *range* = 3.

† (revised) scales are those that have been changed since version 1.0, and their short names are indicated in this manual by a suffix “2” – for example, PF2.

Scoring Algorithm

The QLQ-C30 is composed of both multi-item scales and single-item measures. These include five functional scales, three symptom scales, a global health status / QoL scale, and six single items. Each of the multi-item scales includes a different set of items - no item occurs in more than one scale.

The principle for scoring these scales is the same in all cases:

1. Estimate the average of the items that contribute to the scale; this is the raw score.

2. Use a linear transformation to standardize the raw score, so that scores range from 0 to 100; a higher score represents a higher ("better") level of functioning, or a higher ("worse") level of symptoms.

The technical details are provided below.

If items I_1, I_2, \dots, I_n are included in a scale, the procedure is as follows:

Calculate the raw score (RS) as follows: $RS = (I_1 + I_2 + \dots + I_n)/n$

Apply the linear transformation as follows:

- Functional scales: Scale score = $(1 - ((RS - 1)/range) \times 100$
- Symptom scales / items: Scale score = $(RS - 1)/range \times 100$
- Global health status/QoL: Scale score = $(RS - 1)/range \times 100$

where Range is the difference between the maximum possible value of RS and the minimum possible value. The QLQ-C30 has been designed so that all items in any scale take the same range of values. Therefore, the range of RS equals the range of the item values (see Table 1).

If at least half the components of a scale are present, then the scale score will be calculated using the average of all items answered as the raw score; otherwise the score will be set to missing. For single measures, if the item is missing, the scale score is set to missing.

2. The Medical Outcomes Study-Short Form-36 (SF-36)

■	Subject ID	Quality of Life CLL III Study SF-36 (page 1 of 3)	■								
	

 	 	 	 	

						

 	 	 	 	

				

This survey asks for your views about your health. This information will help you keep track of how you feel and how well you are able to conduct your daily activities.

Answer every questions by selecting the answer as indicated. If you are unsure about how to answer a question, please give the best answer you can. Fill in the circle that best describes your answer.

1. In general, would you say your health is: Excellent Very good Good Fair Poor

2. Compared to one year ago, how would you rate your health, in general, now? Much better now Somewhat better now About the same Somewhat worse now Much worse now

Does your health limit you in the activities listed below? If so, how much?

	Yes, limited a lot	Yes, limited a little	No, not limited at all
3. Vigorous activities, such as running, lifting heavy objects, or participating in strenuous sports?			
4. Moderate activities, such as moving a table, pushing a vacuum cleaner, bowling, or playing golf?			
5. Lifting or carrying groceries?			
6. Climbing several flights of stairs?			
7. Climbing one flight of stairs?			
8. Bending, kneeling, or stooping?			
9. Walking more than a mile?			
10. Walking several blocks?			
11. Walking one block?			
12. Bathing or dressing yourself?			

46547

Subject ID

--	--	--	--

Quality of Life
CLL III Study
SF-36 (page 2 of 3)

Assessment

--	--	--

During the PAST 4 WEEKS, have you had any of the following problems with your work or other regular activities as a result of your PHYSICAL HEALTH?

13. Cut down on the amount of time you spent on work or other activities? Yes No

14. Were limited in the kind of work or other activities? Yes No

15. Accomplished less than you would like? Yes No

16. Had difficulty performing the work or other activities (e.g., it took extra effort)? Yes No

During the PAST 4 WEEKS, have you had any of the following problems with your work or other regular activities as a result of EMOTIONAL PROBLEMS (such as feeling depressed or anxious)?

17. Cut down on the amount of time you spent on work or other activities? Yes No

18. Accomplished less than you would like? Yes No

19. I did not do work or other activities as carefully as usual. True False

20. During the PAST 4 WEEKS, to what extent have your PHYSICAL HEALTH or EMOTIONS interfered with your normal social activities with family, friends, neighbors, or groups?

Not at all A little bit Moderately Quite a bit Extremely

21. How much bodily pain did you have during the PAST 4 WEEKS?

None Very mild Mild Moderate Severe Very severe

22. During the PAST 4 WEEKS, how much did pain interfere with your normal work (including work outside the home and housework)?

Not at all A little bit Moderately Quite a bit Extremely

Subject ID	Quality of Life CLL III Study SF-36 (page 3 of 3)						Assessment
							

For each question, please indicate the one answer that comes closest to the way you have been feeling in the PAST 4 WEEKS...

During the PAST 4 WEEKS, how much of the time....

	All of the time	Most of the time	A good bit of the time	Some of the time	A little bit of the time	None of the time
23. Did you feel full of pep?						
24. Have you been a very nervous person?						
25. Have you felt so down in the dumps that nothing could cheer you up?						
26. Have you felt calm and peaceful?						
27. Did you have a lot of energy?						
28. Have you felt downhearted and blue?						
29. Did you feel worn out?						
30. Have you been a happy person?						
31. Did you feel tired?						
32. Has your HEALTH limited your social activities (like visiting friends or close relatives, etc.)?						

Please choose how TRUE or FALSE these statements are for you.

	Definitely true	Mostly true	Not sure	Mostly false	Definitely false
33. I seem to get sick a little easier than other people.					
34. I am as healthy as anyone I know.					
35. I expect my health to get worse.					
36. My health is excellent.					

Table 2. The SF36 quality of life scoring system and its scales and dimensions

ITEMS	SCALES	Dimensions
3. Vigorous activities		
4. Moderate activities		
5. Lift, carry groceries		
6. Climb several flights	Scale 1: Physical Functioning (PF)	
7. Climb one flight		
8. Bend, kneel		
9. Walk mile		
10. Walk several blocks		
11. Walk one block		
12. Bathe, dress		
13. Cut down time		
14. Accomplished less	Scale 2: Role-Physical (RP)	
15. Limited in kind		
16. Had difficulty		
21. Pain-magnitude	Scale 3: Bodily Pain (BP)	
22. Pain-interfere		
1. General health rating		
36. Excellent	Scale 4: General Health (GH)	
34. As healthy as anyone		
33. Sick easier		
35. Health worse		
23. Pep/life		
27. Energy	Scale 5: Vitality (VT)	
29. Worn out		
31. Tired		
32. Social-extent	Scale 6: Social Functioning (SF)	
20. Social-time		
17. Cut down time		
18. Accomplished less	Scale 7: Role-Emotional (RE)	
19. Not careful		
24. Nervous		
25. Down in dumps	Scale 8: Mental Health (MH)	
26. Peaceful		
28. Blue/sad		
30. Happy		
2. Change in reported health		

